1.2.6 Residual Effect Period

The Residual Effect Period (REP) of the cocktail is 10 days referring to digoxin, the drug with the longest half-life among the cocktail components. This is the period after the last dose with measurable drug levels and/or pharmacodynamic effects still likely to be present.

The Residual Effect Period (REP) [REDACTED] This is the period after the last dose with measurable drug levels and/or pharmacodynamic effects still likely to be present.

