3.3.4 Withdrawal of subjects from treatment or assessments

Subjects may discontinue trial treatment or withdraw consent to trial participation as a whole ('withdrawal of consent') with very different implications; please see Sections [3.3.4.1](#) and [3.3.4.2](#) below.

If a subject is removed from or withdraws from the trial prior to the first administration of trial medication, the data of this subject will not be entered in the case report form (CRF) and will not be reported in the clinical trial report (CTR). If a subject is removed from or withdraws from the trial after the first administration of trial medication, this will be documented and the reason for discontinuation must be recorded in the CRF; in addition, the data will be included in the CRF and will be reported in the CTR. At the time of discontinuation, a complete end of trial examination will be performed, if possible, and the information will be recorded in the CRF. If the discontinuation occurs before the end of the REP (see Section [1.2.3](#)), the discontinued subject should if possible be questioned for AEs and concomitant therapies at or after the end of the REP in order to ensure collection of AEs

and concomitant therapies throughout the REP, if not contrary to any consent withdrawal of the subject.

If it is known that a subject becomes pregnant during the trial, administration of the trial medication is to be stopped immediately, and the subject is to be removed from the trial. The subject is to be followed until she has given birth or until the end of the pregnancy. The subject's data are to be collected until the end of the trial (last visit of last subject) and reported in the CTR. For reporting of pregnancy and associated events, refer to Section [5.2.5.2.4](#).

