3.3.4.1 Discontinuation of trial treatment

An individual subject will discontinue trial treatment if:

1. The subject wants to discontinue trial treatment, without the need to justify the decision
2. The subject has repeatedly shown to be non-compliant with important trial procedures and, in the opinion of both, the investigator and sponsor representative, is not willing or able to adhere to the trial requirements in the future.
3. The subject needs to take concomitant medication that interferes with the investigational medicinal product or other trial treatment
4. The subject can no longer receive trial treatment for medical reasons (such as pregnancy, surgery, adverse events [AEs], or diseases)
5. The subject has an elevation of AST and/or ALT ≥ 3 -fold ULN and an elevation of total bilirubin ≥ 2 -fold ULN (measured in the same blood sample) and/or needs to be followed up according to the DILI checklist provided in the ISF
6. In addition to these criteria, the investigator may discontinue subjects at any time based on his or her clinical judgment.

Even if the trial treatment is discontinued, the subject remains in the trial and, given his/her agreement, will undergo the procedures for early treatment discontinuation and follow up as outlined in the [Flow Chart](#) and Section [6.2.3](#).

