6.2.3 Follow-up period and trial completion

For AE assessment, laboratory tests, recording of ECG and vital signs, and physical examination during the follow-up period, see Sections [5.2.2](#) to [5.2.5](#).

Subjects who discontinue treatment before the end of the planned treatment period should undergo the EoTrial Visit.

All abnormal values (including laboratory parameters) that are assessed as clinically relevant by the investigator will be monitored using the appropriate tests until a return to a medically acceptable level is achieved. (S)AEs persisting after a subject's EoTrial Visit must be followed until they have resolved, have been sufficiently characterised, or no further information can be obtained.

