7.3.4 Safety analyses

Safety will be analysed based on the assessments described in Section [2.2.2.2](#). All treated subjects (TS, refer to Section [7.2](#)) will be included in the safety analysis. Safety analyses will be descriptive in nature and based on BI standards. No hypothesis testing is planned.

For all analyses, the treatment actually administered (= treatment at onset of AE) to the subject will be used (any deviations from the planned treatment will be discussed in the minutes of the Report Planning Meeting).

Treatments will be compared in a descriptive way. Tabulations of frequencies/proportions will be used to evaluate categorical (qualitative) data, and tabulations of descriptive statistics will be used to analyse continuous (quantitative) data.

Measurements (such as ECG, vital signs, or laboratory parameters) or AEs will be assigned to treatments (see Section [4.1](#)) based on the actual treatment at the planned time of the measurement or on the recorded time of AE onset (concept of treatment emergent AEs). Therefore, measurements planned or AEs recorded prior to first intake of trial medication will be assigned to the screening period, those between trial medication intake and end of REP (see Section [1.2.3](#)) will be assigned to the treatment period. Events occurring after the REP but prior to next intake or end of trial termination date will be assigned to 'follow-up'. In case of two or more treatments, the follow-up will be summarized according to the previous treatment. These assignments including the corresponding time intervals will be defined in detail in the TSAP. Note that AEs occurring after the last per protocol contact but entered before final database lock will be reported to Pharmacovigilance only and will not be captured in the trial database.

Additionally, further treatment intervals (analysing treatments) may be defined in the TSAP in order to provide summary statistics for time intervals, such as combined treatments, on-treatment totals, or periods without treatment effects (such as screening and follow-up intervals).

Adverse events will be coded using the Medical Dictionary for Regulatory Activities (MedDRA). Frequency, severity, and causal relationship of AEs will be tabulated by treatment, system organ class, and preferred term. SAEs, AESIs (see Section [5.2.5.1](#)), and other significant AEs (according to ICH E3) will be listed separately.

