On treatment cocktail	Cocktail	Date/time of first administration of the cocktail	Date/time of first administration of BI 730357 or date/time of first administration of the cocktail + Residual effect period (REP) (10 * 24h), whatever occurs earlier
On treatment Cocktail + BI 730357	Cocktail + BI	Date/time of first administration of BI 730357	Date/time of first administration of the cocktail + Residual effect period (REP) (10 * 24h)
On treatment BI 730357	BI	Date/time of first administration of BI 730357 or date/time of first administration of the cocktail + Residual effect period (REP) (10 * 24h), whatever occurs later	Date/time of second administration of the cocktail
On treatment Steady state BI 730357 + cocktail	BI + Cocktail	Date/time of second administration of the cocktail	Date/time of last administration of BI 730357 + Residual effect period (REP) (7 * 24h) Or 12:00 a.m. on day after subject's trial termination date, whatever occurs earlier.
Follow-up	F/U	Date/time of last administration of BI 730357 + REP (7 * 24h)	12:00 a.m. on day after subject's trial termination date

Statistical analyses of [REDACTED] PK parameters will be conducted by treatment period (cocktail vs. BI + cocktail).

More details on the technical implementation of these analyses are provided in the ADS Plan of this TSAP.

According to Section 1.2.6 of the CTP, the REP of the cocktail is 10 days. This is the period after the last dose with measurable drug levels and/or pharmacodynamic effects still likely to be present. [REDACTED]

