7.8 SAFETY ANALYSIS

The safety analyses are described in the CTP Section 7.3.4. All safety analyses will be performed on the TS.

The safety analyses will be descriptive in nature. No hypothesis testing is planned.

CTP 7.3.4:

Measurements (such as ECG, vital signs, or laboratory parameters) or AEs will be assigned to treatments (see Section 4.1) based on the actual treatment at the planned time of the measurement or on the recorded time of AE onset (concept of treatment emergent AEs). Therefore, measurements planned or AEs recorded prior to first intake of trial medication will be assigned to the screening period, those between trial medication intake and end of REP (see Section 1.2.3) will be assigned to the treatment period. Events occurring after the REP but prior to next intake or end of trial termination date will be assigned to 'follow-up'. In case of two or more treatments, the follow-up will be summarized according to the previous treatment. These assignments including the corresponding time intervals will be defined in detail in the TSAP. Note that AEs occurring after the last per protocol contact but entered before final database lock will be reported to Pharmacovigilance only and will not be captured in the trial database.

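### The last on-treatment phase in SAP Table 6.1:1 ignores the second cocktail's 10-day residual effect period, so up to 73 h of it can be labelled follow-up in subjects who stop BI 730357 early

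*SAP*

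**What the plan says.** SAP 6.1, Table 6.1:1, starts the *BI + Cocktail* phase at the second cocktail dose and ends it at "Date/time of last administration of BI 730357 + Residual effect period (REP) (7 * 24h"), or at midnight closing the subject's trial termination date if that is earlier. Follow-up starts at last BI dose + 7 x 24 h. The three earlier on-treatment rows all use first cocktail + 10 x 24 h as a boundary; no row uses the second cocktail + 10 x 24 h.

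The text under the table says: "According to Section 1.2.6 of the CTP, the REP of the cocktail is 10 days". Protocol 1.2.6 is the source: "The Residual Effect Period (REP) of the cocktail is 10 days referring to digoxin".

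The assignment rule is in Protocol 7.3.4 and is repeated in SAP 7.8. For measurements and adverse events (AEs), "those between trial medication intake and end of REP (see Section 1.2.3) will be assigned to the treatment period". SAP 4 states that the planned analyses accord with the revised protocol.

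On early stopping, Protocol 3.3.4.1 says that "the subject remains in the trial and, given his/her agreement, will undergo the procedures for early treatment discontinuation and follow up". Protocol 3.3.4 adds that a subject who discontinues before the end of the REP "should if possible be questioned for AEs and concomitant therapies at or after the end of the REP".

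**The concern.** The same four probe drugs get their own 240 h tail after the first dose and none after the second. On the planned schedule the BI 730357 tail is the longer one and hides the omission. When BI dosing stops soon after the second cocktail, the BI tail ends first, and time that the protocol treats as on treatment becomes follow-up.

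Under SAP 6.1 the AE displays in CTR Section 15 cover only the four on-treatment phases. A new AE starting in the mislabelled hours would be missing from them and from the on-treatment total. It would still appear in Appendix 16.1.13.1.8.1 and in the overall total there. SAP 7.2 also counts a newly started medication as concomitant only if it begins in an on-treatment phase, so treatment begun in those hours would not be counted. An AE that leads to the BI stop is assigned by its onset and stays on treatment. The PK endpoints are not involved.

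**Working it through.** **Inputs.** Time 0 is the second cocktail (Day 1, 09:00; Protocol Flow Chart, Treatment Test).
- Cocktail REP: 10 x 24 = 240 h (Protocol 1.2.6; SAP 6.1).
- BI 730357 REP: 7 x 24 = 168 h (SAP Table 6.1:1; the protocol figure is redacted).
- Scheduled BI doses from Day 1 morning, L: -1, 11, 23, 35, 47, 58.5, 70.5, 82.5, 94.5, 106.5, 118.5 and 130.5 h (Flow Chart).

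**Check of the time scale.** The last planned dose is Day 6, 19:30: 5 x 24 + 19.5 - 9 = 130.5 h, which matches the Flow Chart's 130:30.

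**Formulas.**
- Phase end before the cap = L + 168.
- Break-even with the cocktail REP: L + 168 = 240, so L = 72 h.
- Cap for termination on Day d = midnight ending Day d = 24d - 9 h: Day 7, 159; Day 8, 183; Day 9, 207; Day 10, 231; Day 11, 255.
- Cocktail REP labelled follow-up = max(0, min(240, 24d - 9) - (L + 168)).

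**Example.** Last dose on Day 1 morning, termination on Day 11 or later: 240 - (-1 + 168) = 240 - 167 = 73 h.

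**Hours of cocktail REP labelled follow-up**, by last dose taken and day of termination:

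| Last BI dose | L (h) | L + 168 (h) | Day 7 or earlier | Day 8 | Day 9 | Day 10 | Day 11 or later |
|---|---|---|---|---|---|---|---|
| Day 1 morning | -1 | 167 | 0 | 16 | 40 | 64 | 73 |
| Day 1 evening | 11 | 179 | 0 | 4 | 28 | 52 | 61 |
| Day 2 morning | 23 | 191 | 0 | 0 | 16 | 40 | 49 |
| Day 2 evening | 35 | 203 | 0 | 0 | 4 | 28 | 37 |
| Day 3 morning | 47 | 215 | 0 | 0 | 0 | 16 | 25 |
| Day 3 evening | 58.5 | 226.5 | 0 | 0 | 0 | 4.5 | 13.5 |
| Day 4 morning | 70.5 | 238.5 | 0 | 0 | 0 | 0 | 1.5 |
| Day 4 evening to Day 6 evening (5 doses) | 82.5 to 130.5 | 250.5 to 298.5 | 0 | 0 | 0 | 0 | 0 |

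So 7 of the 12 doses can produce a gap if they are the last one taken. A completer's phase ends at 130.5 + 168 = 298.5 h, which is 298.5 - 240 = 58.5 h past the cocktail REP.

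The 73 h maximum assumes that the Day 1 morning BI dose was taken. If it was missed and the cocktail was still given, the last dose is at -13 h and the gap is 240 - 155 = 85 h.

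**The case against.** The strongest reply is that the gap needs a chain of events in a 15-subject trial: BI stopped within 72 h of the second cocktail, termination late enough, and a new AE in the leftover hours. Protocol 3.3.4 places an end-of-trial examination at discontinuation if possible, and Protocol 6.2.3 says: "Subjects who discontinue treatment before the end of the planned treatment period should undergo the EoTrial Visit". Protocol 5.2.5.2.1 ends CRF entry of AEs at the subject's end of trial. If termination is set at that examination, the cap closes the phase and there is no follow-up interval. This stands, and it limits the size of the problem. It does not exclude the case: a subject may stop treatment and remain in the trial, AE questioning is sought at or after the end of the REP, and the Flow Chart's only follow-up visit is on Days 14 to 22, after 240 h.

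Three further replies carry less weight.
- Protocol 7.3.4 leaves the exact intervals to the SAP and does not say which REP governs when several drugs are active. Delegating the detail does not license cutting short a REP that both documents put at 10 days.
- Protocol 7.3.4 also summarises follow-up by the previous treatment and lists serious and other significant AEs separately. That keeps such events visible, but does not return them to the on-treatment tables. SAP 7.8.1 assigns AEs up to last drug intake + REP to on-treatment phases, but as defined in this same table.
- The text after the REP sentence in SAP 6.1 is redacted, and the ADS Plan cited there is not available. A correction may exist in either place, but the table cells would still need to agree with it.

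**Conclusion.** The concern holds for the table as written: the second cocktail's 240 h REP is missing from the end of *BI + Cocktail* and from the start of follow-up, which conflicts with Protocol 7.3.4 for some early BI stoppers. Two conditions are both needed: last BI dose less than 72 h after the second cocktail, and termination later than last BI dose + 168 h. The mislabelled time is then at most 73 h on scheduled dose times, provided the Day 1 morning dose was taken.

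Severity is minor. Completers are unaffected, the consequence is confined to descriptive safety summaries, and the documents give no early-stop rate, so the number of subjects affected cannot be estimated and may be zero.

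**What to change.** In Table 6.1:1, end *BI + Cocktail* at the later of last BI 730357 dose + 7 x 24 h and second cocktail + 10 x 24 h, keep the existing termination cap, and start follow-up at that later time. Bring the ADS Plan into line. The mislabelled time becomes 0 h for every possible last dose, and the completer's phase end stays at 298.5 h.

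The cost is one phase-end cell, the follow-up start and the derivation code. There is one trade-off: for early stoppers the last hours of the phase (up to 73 h) would be residual cocktail time only, although SAP 6.1 describes the phase as having BI at steady state. A table footnote can say so. The change concerns an analysis label only and alters no dosing or clinical procedure.

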6.2 IMPORTANT PROTOCOL DEVIATIONS

Table 6.2: 1 Handling of important protocol deviations (iPDs)

iPD code	iPD Category & Brief Description	Excluded from which analysis set
A1	Inclusion Criteria Not Met	None
A2	Exclusion Criteria violated	None
B1	Informed consent not available/not done	TS, PKS [REDACTED]
B2	Informed consent too late	None
C1	Incorrect trial medication intake	PKS [REDACTED]
C3	Non-compliance	PKS [REDACTED]
C4	Medication code broken inappropriately	None
C5	Incorrect intake of trial medication	PKS [REDACTED]
C6	Improper washout between treatments	PKS [REDACTED]
D1	Prohibited medication use	PKS [REDACTED]
D2	Mandatory medication not taken	PKS [REDACTED]
D3	Improper washout of concomitant medication	PKS [REDACTED]
E1	Certain violations of procedures used to measure primary or secondary data	PKS [REDACTED]
F1	Certain violations of time schedule used to measure primary or secondary data	PKS [REDACTED]
G1	Incorrect intake of meal	PKS [REDACTED]

Table 6.2: 2 Handling of non-important COVID-19 related protocol deviations

PD code	PD Category	Excluded from which analysis set
Q1	Missed examination	None
Q2	(Partially) missed visit	None
Q3	Drug shipment	None

Consistency check listings (for identification of deviations from time windows) and a list of protocol deviations (e.g. deviations in drug administration, in blood sampling times, etc.) will be provided to be discussed at the Report planning meeting (RPM). At this meeting, it will be decided whether a discrepant data value can be used in analyses or whether it must be corrected in the clinical database. Each protocol deviation must be assessed to determine whether it is an iPD and whether it is COVID-19 related. For definition of iPDs, and for the process of identification of these, refer to the BI reference document "Identify and Manage Important Protocol Deviations (iPD)" ([1](#)).

If any iPDs are identified, they are to be summarised into categories and will be captured in the RPM minutes. Categories which are considered to be iPDs in this trial are defined in the integrated quality and risk management plan (IQRMP). If the data show other iPDs, the definition in the IQRMP will be supplemented accordingly by the time of the RPM.

iPDs will be summarised and listed. Additionally, protocol deviations associated with COVID-19 disruption (non-important and important protocol deviations) will be summarised and listed.

6.3 SUBJECT SETS ANALYSED

The following subject sets will be defined for statistical analysis:

- Treated set (TS):

The treated set includes all subjects who signed informed consent and were treated with at least one dose of study drug.

The treated set will be used for safety analyses.

- Pharmacokinetic parameter analysis set (PKS):

This set includes all subjects in the TS who provide at least one PK endpoint that was defined as primary or secondary and was not excluded due to a protocol deviation relevant to the evaluation of PK or due to PK non-evaluability (as specified in the subsection 'Pharmacokinetics' in section 7.3 in the CTP). Thus, a subject will be included in the PKS, even if he/she contributes only one PK parameter value for one period to the statistical assessment.

[figure not shown]
Descriptive and model based analyses of PK parameters will be based on the PKS. Thus, the primary and secondary analyses will be based on the PKS.

Relevant protocol deviations may be

- Incorrect trial medication taken
- Incorrect dose of trial medication taken
- Use of restricted medications

Plasma concentrations and/or parameters of a subject will be considered as non-evaluable, if for example

- The subject experienced emesis that occurred at or before two times median tmax of the respective treatment (Median tmax is to be determined excluding the subjects experiencing emesis),
- A predose concentration of BI 730357 is >5% Cmax value of that subject in the respective treatment period
- Missing samples/concentration data at important phases of PK disposition curve

The discussion of all exceptional cases and problems and the decisions on the allocation of subjects to analysis sets will be made at latest at the RPM.

Table 6.3: 1 Subject sets analysed

Class of endpoint	TS	Subject set	
		PKS	
Disposition	x		
Treatment exposure	x		
IPDs	x		
Demographics/baseline endpoints	x		
Safety parameters	x		
PK endpoints		x	

6.5 POOLING OF CENTRES

This section is not applicable, because the study was performed in only one centre.

6.6 HANDLING OF MISSING DATA AND OUTLIERS

In CTP Section 7.5 the handling of missing data is defined.

Data of screened subjects who were withdrawn from the trial prior to first administration of any study drug will not be reported in the CTR.

Data of subjects who failed to complete all periods of the study (dropouts or withdrawals) will be reported in the CTR as far as their data are available. All withdrawals will be documented and the reason for withdrawal recorded in the CTR.

It is not planned to impute missing values for safety parameters.

The only exceptions where imputation might be necessary for safety evaluation are AE dates. Missing or incomplete AE dates are imputed according to BI standards (2).

Missing data and outliers of PK data are handled according to the relevant BI internal procedures. PK parameters that cannot be reasonably calculated based on the available drug concentration-time data will not be imputed. PK data will be excluded of analysis as described in Section 7.3 of the CTP.

6.7 BASELINE, TIME WINDOWS AND CALCULATED VISITS

Baseline will be defined as the last available value before the administration of the cocktail in period 1 (Visit 2). Note that this baseline definition will be used for evaluation of data of all on-treatment periods (“cocktail”, “BI + cocktail”, “BI”, “cocktail + BI”, as defined in Section 6.1).

Time windows are defined in Section 6.1 of the CTP. Adherence to time windows will be checked at the RPM.

Unscheduled measurements of laboratory data or vital signs data will be assumed to be repeat measurements of the most recent scheduled measurement (e.g. for follow-up or confirmation of a particular value). Therefore, unscheduled measurements will be assigned to the planned time point of the previous scheduled measurement. Descriptive statistics of on-treatment laboratory data will be calculated by planned time point based on the worst value of the subject at that planned time point (or assigned to that planned time point). For vital signs, descriptive statistics will be calculated by planned time point based on the last value of the subject at that planned time point (or assigned to that planned time point).

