5.2.5.1.4 Adverse events of special interest

The term adverse events of special interest (AESI) relates to any specific AE that has been identified at the project level as being of particular concern for prospective safety monitoring and safety assessment within this trial, e.g. the potential for AEs based on knowledge from other compounds in the same class. AESIs need to be reported to the sponsor’s Pharmacovigilance Department within the same timeframe that applies to SAEs, please see Section [5.2.5.2.2](#).

The following are considered as AESIs:

- Hepatic injury
A hepatic injury is defined by the following alterations of hepatic laboratory parameters:
 - o An elevation of AST (aspartate transaminase) and/or ALT (alanine transaminase) ≥ 3 -fold ULN combined with an elevation of total bilirubin ≥ 2 -fold ULN measured in the same blood sample, or
 - o Aminotransferase (ALT, and/or AST) elevations ≥ 10 fold ULN

These lab findings constitute a hepatic injury alert and the subjects showing these lab abnormalities need to be followed up according to the 'DILI checklist' provided in the ISF. In case of clinical symptoms of hepatic injury (icterus, unexplained encephalopathy, unexplained coagulopathy, right upper quadrant abdominal pain, etc.) without lab results (ALT, AST, total bilirubin) available, the Investigator should make sure that these parameters are analyzed, if necessary in an unscheduled blood test. Should the results meet the criteria of hepatic injury alert, the procedures described in the DILI checklist should be followed.

- Severe infections (grading according to Rheumatology Common Toxicity Criteria [RCTC] developed by OMERACT [[R13-3515](#)])
- Opportunistic and mycobacterium tuberculosis infections

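### SAP 6.7 carries unscheduled laboratory and vital-sign values back to the previous planned time point even when a new treatment has started in between, so some post-dose values are tabulated before that treatment

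*SAP*

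**What the plan says.** SAP 6.7 rests on one assumption: "Unscheduled measurements of laboratory data or vital signs data will be assumed to be repeat measurements of the most recent scheduled measurement". The assignment follows from it: "unscheduled measurements will be assigned to the planned time point of the previous scheduled measurement". Neither sentence makes an exception for a dose given between the two measurements.

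The value that represents a time point is then chosen by type of data. For laboratory data: "Descriptive statistics of on-treatment laboratory data will be calculated by planned time point based on the worst value of the subject". For vital signs the summary is "based on the last value of the subject at that planned time point". In both cases, values assigned to the time point count as belonging to it. Baseline is the last available value before the period 1 cocktail and serves all on-treatment phases.

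SAP 7.8, repeating Protocol 7.3.4, attributes measurements to treatment "based on the actual treatment at the planned time of the measurement". Protocol 7.3.4 adds that "measurements planned or AEs recorded prior to first intake of trial medication will be assigned to the screening period".

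Two other parts of the SAP use actual times. Table 6.1:1 bounds the analysis phases by the date and time of dosing, and SAP 7.8.1 attributes adverse events by recorded onset.

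**The concern.** The repeat-measurement assumption suits a retest of a doubtful value. It does not suit a measurement taken because something happened after a new drug was given. The protocol foresees such measurements: when clinical signs of hepatic injury appear without results at hand, the liver parameters are to be analysed "if necessary in an unscheduled blood test".

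If a treatment started between the last scheduled measurement and the unscheduled one, the rule gives the later value a planned time before that treatment. Attribution by planned time then also gives it the earlier treatment. An abnormality 12 h after the second cocktail could appear as an adverse event under 'BI + Cocktail' while the laboratory value behind it sits at -74:00, under an earlier phase. At stake is whether the by-time-point, change-from-baseline and by-treatment safety tables show such values where they occurred.

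**Working it through.** The plan states no figure on this point. The check applies the SAP 6.7 rule to the planned times.

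**Inputs**
- Flow Chart, Treatment Reference: cocktail at 0:00. Routine labs are set A at screening (Day -21 to -2) and set B at 24:00. A footnote limits the Day -1 laboratory mark to drug, alcohol and pregnancy tests, so no routine lab falls on Day -1 or before dosing on Day 1. Vital signs at -2:00, 1:00, 2:00, 4:00 and 24:00.
- Flow Chart, Treatment Test: first BI 730357 dose at -170:00, cocktail at 0:00. Set B at -170:00, -74:00, 24:00 and 95:00. Vital signs at -170:30, -74:30, -2:00, 1:00, 2:00, 4:00, 8:00 and 24:00.

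**Formula**
- Filed at = last scheduled measurement at or before the dose.
- Window = first scheduled measurement after the dose minus time of dose.

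| Data | Treatment start | Filed at | Window |
|---|---|---|---|
| Labs | Cocktail 1 (0:00) | Screening | 24:00 - 0:00 = 24 h |
| Labs | First BI 730357 (-170:00) | -170:00 | -74:00 - (-170:00) = 96 h |
| Labs | Cocktail 2 (0:00) | -74:00 | 24:00 - 0:00 = 24 h |
| Vital signs | Cocktail 1 (0:00) | -2:00 | 1:00 - 0:00 = 1 h |
| Vital signs | First BI 730357 (-170:00) | -170:30 | -74:30 - (-170:00) = 95.5 h |
| Vital signs | Cocktail 2 (0:00) | -2:00 | 1:00 - 0:00 = 1 h |

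**Reading the rows**
- Labs after cocktail 1: the assigned time precedes any trial medication, so the value is classed as screening. The worst-value rule covers on-treatment labs only, so the value leaves those statistics.
- Labs after cocktail 2: the value stays on treatment but is shown three days early, before the combination.
- Vital signs, all three rows: the assigned time is before the dose. As the last value at that time point, the post-dose reading replaces the true pre-dose one.
- Labs after the first BI 730357 dose: the planned lab time equals the planned dose time, so the documents do not settle whether the time point is before or after the dose.

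**Totals per subject**
- Labs: 24 + 24 = 48 h firm, and a further 96 h unclear.
- Vital signs: 1 + 1 + 95.5 = 97.5 h.

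**Illustration with assumed values, all 15 subjects contributing**
- One subject has ALT 25 U/L at -74:00 and an unscheduled 150 U/L within 24 h of cocktail 2. The -74:00 mean rises by (150 - 25)/15 = 8.3 U/L.
- One subject has an unscheduled systolic pressure 40 mmHg lower 30 min after a cocktail. The -2:00 mean falls by 40/15 = 2.7 mmHg.

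**The case against.** **The important values are captured elsewhere.** Clinically relevant laboratory and vital-sign changes are reported as adverse events, hepatic injury is an adverse event of special interest with its own table, and both are attributed by onset. Out-of-range labs are highlighted in listings. This stands, and it confines the problem to descriptive tables. It does not correct those tables.

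**Baseline is not contaminated.** A reader might infer that a reading 30 min after cocktail 1 becomes the baseline. The text does not support that: baseline must precede the cocktail, and a post-dose reading does not. It would be at risk only if programmed from the assigned planned time.

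**The change under BI 730357 is not cancelled.** A reader might infer that a carried-back value shrinks a Day -7 to Day -3 change. No such contrast is planned. Differences are taken from the period 1 baseline, so a lab filed at Day -7 still shows as a rise, with an early label.

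**The full 144 h of laboratory time is not firmly misplaced.** For 96 of those hours the value goes to the dose's own nominal time. These windows are also elapsed time, not a frequency: the documents give no rate of unscheduled measurements.

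**A general bias toward no effect does not follow.** That is the likely direction when abnormal values are carried back, but it is not certain, and no hypothesis test is planned.

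**A safeguard may exist elsewhere.** Table 6.1:1 uses actual times, and SAP 6.1 refers to an ADS Plan that is not available here; laboratory displays follow a sponsor standard that is also not available. Either might contain a restriction. The SAP rule as written contains none, and the visible text does not reconcile it with Table 6.1:1.

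**Conclusion.** The point holds in limited form and is worth correcting. As written, SAP 6.7 together with attribution by planned time places some post-dose values before the treatment they followed. The firm windows are 48 h per subject for labs and 97.5 h for vital signs; the 96 h of labs after the first BI 730357 dose are ambiguous.

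The consequence is confined to descriptive laboratory and vital-sign tables by time point, change from baseline and treatment. Adverse event and special-interest event tables, ECG findings, the PK analyses and a baseline determined by actual time are untouched. With 15 subjects, a single carried-back value can visibly move a mean, but how many would occur is unknown.

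This conclusion assumes that the Flow Chart times are read correctly from partly broken columns and that no unseen programming document overrides the rule.

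**What to change.** Amend SAP 6.7 as follows:
- Carry an unscheduled value back only if none of three events lies between it and the previous scheduled measurement: first cocktail, first BI 730357 dose, second cocktail.
- Otherwise assign it to the next planned time point, provided no further one of these administrations intervenes. If there is no such time point, report the value as unscheduled.
- In all cases take the analysis phase from the actual date and time, as in Table 6.1:1.

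The barrier should be these three administrations and not every phase start in Table 6.1:1. Some phases begin or end when the 10-day residual effect period of the cocktail runs out, which is not a dose and should not block a genuine repeat. The 'Cocktail + BI' phase may also be too short to contain a later planned lab.

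With this change every window in the table above falls to 0 h, including the ambiguous one. No sample size, error rate or primary analysis changes.

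The cost is a short SAP amendment and one programming condition. A few values will appear at the following time point or only as unscheduled. A vital sign moved forward will usually be superseded by the scheduled reading under the last-value rule; it then no longer distorts the pre-dose summary, but it is not the value summarised at the later time point either.
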